7.1.9 PROCEDURES FOR DOCUMENTING PREGNANCY DURING STUDY

Subjects who are pregnant or expect to become pregnant during the course of the study up to 6 months following the last study treatment of investigational product will be excluded from participation in the study. Should a subject become pregnant after enrolling in the study, she will not be given any further study treatments. A Pregnancy Form will be completed by the site personnel and submitted to the sponsor study team and medical monitor within 24 hours after learning of the pregnancy. The investigator will also report this event to the IRB within 24 hours of becoming aware of the pregnancy. Sites must request the subject's permission to query pregnancy outcome and follow each subject to determine the outcome of the pregnancy. Results will be summarized in the clinical study report (CSR).

Subjects who become pregnant at any point during the study will continue to be followed for safety assessments without receiving further study treatment. Procedures that are contraindicated during pregnancy, including additional treatments, must not be performed. Investigators should use clinical judgment regarding subsequent study-related blood collection based on the presence or absence of anemia in each subject. Subjects who are not withdrawn will continue to be followed for safety assessments to study discharge per protocol.

All pregnancies that occur from the time of first study treatment through the follow up visits must be reported. The investigator will monitor the subject and follow the outcome of the pregnancy. If the end of the pregnancy occurs after the study has been completed, the outcome will be reported directly to the study team and the medical monitor.

7.2 METHODS AND TIMING OF THE COLLECTION AND RECORDING OF SAFETY DATA

Non-serious AEs and SAEs (and UADEs) will be collected for each subject from the time when informed consent is obtained through Week 88.

The sources of AEs cover:

- 1. The subject's response to questions about her health (a standard non-leading question such as 'How have you been feeling since your last visit?' is asked at each visit).
- 2. Symptoms spontaneously reported by the subject.

- Evaluations and examinations where the findings are assessed by the investigator to be clinically significant changes or abnormalities.
- Other information relating to the subject's health becoming known to the investigator (e.g. hospitalization).

All AEs will be reported on the appropriate CRF. Any SAE (or UADE) occurring during the course of the study must be reported to the sponsor within 24 hours of awareness.

7.3 SAFETY AND TOXICITY MANAGEMENT

The Medical Monitor will be responsible for the overall safety monitoring of the study.

Safety assessments include the following:

- Incidence of all adverse events classified by system organ class (SOC), preferred term, severity, and relationship to study treatment
- Changes in safety laboratory parameters (e.g., hematology, serum chemistry, and urinalysis)
- Local and systemic injection site review; special attention will be paid to the examination of the injection site. Administration site reactions and the subject's complaints will be documented.

[figure not shown]
7.3.1 EVENTS REQUIRING EXPEDITED REPORTING

Events requiring expedited reporting (ERER) will be defined as related adverse events due to VGX-3100X/placebo delivered with CELLECTRA[™] 5PSP that meets any of the following criteria:

- Grade 3 or greater administration site erythema, and/or induration recorded ≥ 2 hours after Study Treatment
- Grade 4 or greater administration site pain, tenderness recorded ≥ 2 hours after Study Treatment
- Grade 3 or greater fever
- Grade 3 or greater systemic symptoms, including generalized pruritus

As per the Toxicity Grade for Healthy Adults and per CTCAE v 4.03. The most severe grade for that particular event is to be documented in the CRFs.

Sites will inform the Sponsor vial email and to designee vial phone or fax of any ERER within 24 hours to discuss whether further dosing should continue by contacting Inovio as follows.

7.3.2 STOPPING RULES (CRITERIA FOR PAUSING OF STUDY)

If at any time during a study one-third (1/3) or more of the subjects experience an ERER, further
enrollment and study treatment will be halted immediately until a thorough investigation has
been conducted by the Medical Monitor, Principal Investigator for the trial, and the DSMB.
Only the DSMB may review unblinded data in making their recommendation to the Sponsor
regarding continuation of a trial.

- If any SAE (or potentially life-threatening AE), or death assessed as related to study treatment occurs, further enrollment and study treatment will be halted immediately until a thorough investigation has been conducted by the Medical Monitor, Principal Investigator for the trial, IRB (if applicable) and the DSMB.
- If three or more subjects in this study, experience the same Grade 3 or 4 adverse event, assessed as related to study treatment, further enrollment and study treatment will be halted immediately until a thorough investigation has been conducted by the Medical Monitor, Principal Investigator for the trial, and the DSMB.
- In the event of two identical, unexpected, Grade 4 toxicities, assessed as related to study treatment, further enrollment and study treatment will be halted immediately until a thorough investigation has been conducted by the Medical Monitor, Principal Investigator for the trial, IRB (if applicable) and the DSMB.

The sponsor or designee will notify all investigators and IRBs/EC (if required) regarding the outcome of any investigation stemming from a Study Pause.

Guidelines for assessing relatedness are detailed in Section 7.1.6.

8 STATISTICAL ANALYSIS PLAN

8.1 GENERAL CONSIDERATIONS

The statistical analysis of the data will be performed by Inovio Pharmaceuticals or its representative.

This is a two-arm, multi-center, placebo-controlled, blinded, and randomized clinical trial in subjects with a histologic diagnosis of cervical HSIL. The study's primary endpoint is binary: regression to CIN1/normal and clearance of HPV-16 and/or 18 infection from cervical tissue based on tissue collected at Week 36. The primary hypothesis is that VGX-3100X will be superior to placebo regarding the proportion who achieve the primary endpoint. Secondary efficacy analyses involve regression to CIN1/normal, clearance of HPV-16 and/or 18 infection from cervical tissue and non-progression of cervical lesions. Other secondary analyses concern safety and humoral and cellular immunological measures. Exploratory analyses concern tissue immunological measures, durability of clearance of HPV-16 and/or 18 infection from cervical tissue, clearance of HPV-16 and/or 18 infection from non-cervical tissue, effect of HLA type on efficacy, association of colposcopy, cytology, and virology and efficacy, and patient-reported outcomes.

8.2 RANDOMIZATION AND BLINDING

Subjects will be randomized (2 VGX-3100X:1 Placebo) in a stratified manner according to a) the degree of CIN observed in the biopsy specimens at screening (CIN2 vs. CIN3), b) BMI category (≤25 vs. >25 kg/m²), and c) age category (<25 years vs. ≥25 years). There will be no pre-determined number of subjects required to be randomized within each stratum. To ensure that milder CIN2 disease is not overrepresented in the study, the percentage of subjects enrolled with CIN2 will not exceed 50% of the total enrolled.

The study is double-blinded.

8.3 SAMPLE SIZE/POWER

A sample of 165 subjects will be randomized to receive either 6 mg VGX-3100X or placebo IM followed by EP in a 2:1 ratio. This sample size provides 90% power to declare VGX-3100X superior to placebo, assuming the true proportion of subjects who achieve the primary endpoints is 40% and 15% for VGX-3100X and placebo, respectively, and assuming 90% evaluability from randomization. These assumptions are based on the mITT result from the Phase 2 study.

8.4 ANALYSES POPULATIONS

Analysis populations will include:

- The modified intention to treat (mITT) population includes all subjects who receive at least one dose of Study Treatment. Subjects in this sample will be grouped to treatment arms as randomized. Analysis of the mITT population will be primary for the analysis of efficacy in this study.
- The per-protocol (PP) population comprises subjects who receive all doses of Study Treatments and have no protocol violations. Subjects in this sample will be grouped to treatment arms as randomized. Analyses on the PP population will be considered supportive of the corresponding mITT population for the analysis of efficacy. Subjects excluded from the PP population will be identified and documented prior to unblinding of the study database.
- The safety analysis set includes all subjects who receive at least one does of Study Treatment. Subjects will be analyzed as to the treatment they received.

Subjects who do not complete the study will not be replaced.

8.5 SUBJECT DISPOSITION

Disposition will be summarized by treatment arm for all randomized subjects and will include the number and percentage randomized, the number and percentage who received each dose and the number who completed the trial. The number and percentage of subjects who discontinued will be summarized overall and by reason. The number in each analysis population will also be presented.

8.6 DEMOGRAPHIC AND OTHER BASELINE CHARACTERISTICS

Demographic and baseline data will be summarized with descriptive statistics: mean standard deviation, minimum, median, and maximum values for continuous variables, and percentages for categorical variables, by treatment arm, for the mITT population. Prior and concomitant medications will also be summarized with percentages in this fashion.

8.7 MEDICAL HISTORY

The percentage of subjects with abnormal medical history findings will be summarized by body system, by treatment arm, for the mITT population.

8.8 PRIOR AND CONCOMITANT MEDICATIONS

Prior medications are those that were used before the start of the trial (prior to Day 0). Concomitant medications are those used during the course of the trial (on or after Day 0). Partial start dates of prior and concomitant medications will be assumed to be the earliest possible date consistent with the partial date. Partial stop dates of prior and concomitant medications will be assumed to be the latest possible

date consistent with the partial date. Data for all prior and concomitant medications will be summarized with percentages by treatment arm, for the mITT population.

8.9 EFFICACY ANALYSES

The true treatment effect on the primary endpoint is $\delta = p_V - p_P$, where p_V and p_P denote the true population probabilities of the primary endpoint for VGX-3100X and Placebo, respectively. The primary hypothesis of superiority is:

$$H_0$$
: $\delta \leq 0$ vs. H_1 : $\delta > 0$.

A p-value for this hypothesis test and corresponding 95% confidence interval will be computed based on the method of Miettinen and Nurminen [27]. Superiority will be concluded if the one-sided p-value is <0.025 and the corresponding lower bound of the 95% CI exceeds zero.

The secondary efficacy endpoints will be analyzed in the same manner as the primary hypothesis, but without the hypothesis test p-values.

The histopathologic efficacy time frame is defined by those who have undergone a biopsy or surgical excision at any time starting from 14 days prior to the protocol-specified target date of Week 36. It also includes subjects who underwent early intervention prior to this time frame; these subjects are considered as failures for the efficacy endpoints. Table 13 provides details for the definition of the primary endpoint response.

Table 13. Definition of Primary Endpoint Responder and Non-Responder

Responder	Non-Responder
Subject with no histologic evidence of cervical HSIL ^a at Week 36 evaluation and no evidence of HPV-16 or HPV-18 at Week 36 AND	Subject with histologic evidence of cervical HSIL, AIS, cervical carcinoma at Week 36 evaluation OR Subject with evidence of HPV-16 or HPV-18 at Week 36
Subject in which a cervical tissue sample was NOT obtained between collection of tissue to determine entry eligibility up to Week 36 primary endpoint visit	OR Subject in which an additional cervical tissue sample was obtained between collection of tissue to determine entry eligibility up to Week 36 primary endpoint visit

^a no evidence of HSIL is defined by histology as negative, squamous atypia, or LSIL

Exploratory analyses will examine the relationship between the primary efficacy endpoint and a) HLA results, b) colposcopy results, c) cytology results, and d) HPV results. As each of these results are categorical, relationships will be examined with contingency tables and logistic regression models which model the primary endpoint versus these results and treatment group as regressor variables.

Other exploratory analyses will examine durability of clearance of HPV-16 and/or 18 infection from cervical tissue at Weeks 62 and 88, and clearance of HPV-16 and/or 18 infection from non-cervical tissue.

Descriptive statistics will be utilized; percentages of subjects who cleared will be presented by time point or anatomic location and treatment group.

8.10 IMMUNOGENICITY ANALYSES

Post-baseline cellular and humoral response magnitude may be compared between treatment groups using a difference in medians and associated non-parametric 95% CI. Post-baseline tissue response magnitude will be compared between treatment groups using a difference in means and associated t-distribution based 95% CIs.

Valid samples for statistical analysis purposes will be those collected within 7 or 14 days of the specified time points (see Table 1). Baseline is defined as the last measurement prior to the first treatment administration.

8.11 SAFETY ANALYSES

8.11.1 ADVERSE EVENTS

All AEs will be summarized among the safety population by frequency per treatment arm. These frequencies will be presented overall and separately by dose, and will depict overall, by system organ class and by preferred term, the percentage of subjects affected. Additional frequencies will be presented with respect to maximum severity and to strongest relationship to Study Treatment. Multiple occurrences of the same AE will be counted only once following a worst-case approach with respect to severity and relationship to Study Treatment. All serious AEs will also be summarized as above.

The main summary of safety data will be based on events occurring within 14 days of any dose. For this summary, the frequency of preferred term events will be compared between study arms with risk differences and 95% confidence intervals, using the method of Miettinen and Nurminen [27]. As this analysis will use many event categories, and produce many confidence intervals, caution should be exercised when interpreting these confidence intervals. Separate summaries will be based on events occurring within 7 days of any dose and regardless of when they occurred.

Any AEs with a missing or partial onset date will be included in the overall AEs, but not be included within specified day-range summaries. AE duration will be calculated as (Stop Date – Start Date) + 1.

8.11.2 LABORATORY DATA

Continuous response variables per time point and changes from baseline will be summarized with mean, median, minimum, and maximum values, and categorical response variables will be summarized per time point with percentages, by treatment arm. Baseline is defined as the last measurement prior to the first treatment administration.

8.12 VITAL SIGNS

Measurements for vital signs as well as changes from baseline will be summarized with descriptive statistics: mean standard deviation, minimum, median, and maximum values by time point and treatment arm, for the mITT population. Baseline is defined as the last measurement prior to the first treatment administration.

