6.3.3 SAFETY EVALUATIONS

6.3.3.1 Physical Exam

A full physical examination (PE) will be conducted during screening and study discharge. It will include an assessment of the following: general appearance, skin, head, eyes, ears, nose, and throat, and lymph nodes, and respiratory, cardiovascular, gastrointestinal, genitourinary, musculoskeletal, and neurological systems.

A targeted physical assessment will be performed at other visits as determined by the investigator or directed per subject complaints. The injection site is to be assessed by the study personnel at 30 minutes after each study treatment.

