8.13 PHYSICAL EXAMINATION

The percentage of subjects with abnormal physical examination findings at each time point will be summarized by treatment arm and by body system, for the mITT population.

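### Protocol v2.0 and v2.1 summarise vital signs and physical examinations in the as-randomised mITT population, although adverse events use the as-treated safety set

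*Protocol*

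**What the plan says.** Section 8.4 (v2.0, repeated in v2.1) defines two populations that matter here.

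- mITT: "The modified intention to treat (mITT) population includes all subjects who receive at least one dose of Study Treatment". Its grouping and purpose follow: "Subjects in this sample will be grouped to treatment arms as randomized. Analysis of the mITT population will be primary for the analysis of efficacy".
- Safety: "The safety analysis set includes all subjects who receive at least one does of Study Treatment". Its grouping rule is "Subjects will be analyzed as to the treatment they received".

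Section 8.11.1 applies the second set to adverse events: "All AEs will be summarized among the safety population by frequency per treatment arm".

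Sections 8.12 and 8.13 apply the first. Vital signs, and their changes from baseline, are given as mean, standard deviation, "minimum, median, and maximum values by time point and treatment arm, for the mITT population". The percentage of women with abnormal examination findings at each time point "will be summarized by treatment arm and by body system, for the mITT population".

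Physical examination (6.3.3.1) and vital signs (6.3.3.2) both stand under the heading "6.3.3 SAFETY EVALUATIONS".

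**The concern.** The two populations contain the same women. The only thing the safety set adds is that a woman is counted under the product she received. Section 8.4 therefore already provides for dosing errors, and 8.12 and 8.13 drop that provision for two kinds of post-dose safety data.

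What is at stake is whether the safety tables agree with each other. A woman randomised to placebo who received VGX-3100X could have an adverse event counted under VGX-3100X while the abnormal examination or vital sign behind it is counted under placebo. A reader comparing the tables could not reconcile them. If the product does affect these measures, counting an exposed woman in the placebo column, or the reverse, tends to shrink the visible difference between arms. For safety data that is the unhelpful direction.

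**Working it through.** The plan gives no figure on this point, so there is none to reproduce. The check is a comparison of sections, followed by a bound on the size.

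**Sections side by side (v2.0 and v2.1)**

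| Data | Section | Population | Members | Grouping |
|---|---|---|---|---|
| Adverse events | 8.11.1 | Safety | At least one dose | As treated |
| Vital signs | 8.12 | mITT | At least one dose | As randomised |
| Physical examination | 8.13 | mITT | At least one dose | As randomised |

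Membership is the same in every row and grouping is not. The tables can therefore differ only for a woman whose received product differs from her assigned one.

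**Arm sizes.** Section 8.3 of these versions randomises 165 women 2:1: 165 × 2/3 = 110 to VGX-3100X and 165 × 1/3 = 55 to placebo. I assume that all are dosed and examined.

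**Denominators.** The number mis-dosed, k, is an assumption, because the documents give no rate. If k women randomised to placebo receive VGX-3100X, then:

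| k | mITT (VGX-3100X / placebo) | Safety set (VGX-3100X / placebo) |
|---|---|---|
| 0 | 110 / 55 | 110 / 55 |
| 1 | 110 / 55 | 111 / 54 |
| 2 | 110 / 55 | 112 / 53 |
| 3 | 110 / 55 | 113 / 52 |

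**Size in 8.13, one mis-dosed woman with an abnormal finding.** Let x be the number of abnormal findings in her assigned placebo column, hers included.

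- Placebo percentage as randomised: x/55. As treated: (x − 1)/54.
- Difference: x/55 − (x − 1)/54 = (55 − x)/(55 × 54).
- This is largest at x = 1, giving 54/(55 × 54) = 1/55 = 1.8 percentage points.

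For a woman assigned VGX-3100X who receives placebo, the same algebra on the VGX-3100X column gives (110 − y)/(110 × 109), where y counts the abnormal findings there. It is largest at y = 1: 1/110 = 0.9 points.

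**Size in 8.12.** Vital signs are reported as mean, standard deviation, minimum, median and maximum. Moving one woman changes those values by an amount that depends on her readings, and no percentage-point figure applies.

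**Effect of correcting it.** Because membership is unchanged, no woman enters or leaves any table. Efficacy analyses, sample size and power are not touched.

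**The case against.** The strongest case against has five parts.

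1. *The text may be superseded.* The latest version is v3.0, and the available text of it stops in Section 6.1.1. Its summary of changes says that the primary analysis moved from mITT to ITT and that Section 8 was modified. Its contents page still lists 8.12 and 8.13, and no change to them is mentioned, but the summary covers only significant changes. This stands as a limit. A reader might infer that the current version has the defect, but the documents neither show that nor rule it out.

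2. *The effect depends on a dosing error.* No misallocation is reported and no rate is expected. This stands. With three doses, a single error would also give mixed exposure, and Section 8.4 does not say which arm such a woman then belongs to. The tables conflict only when she is classed under a product other than the one assigned.

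3. *Important findings already reach the as-treated tables.* Section 7.1.7 requires abnormal assessments, vital signs included, to be recorded as adverse events when they come with signs or symptoms and meet the definition. Section 7.2 makes clinically significant examination findings a source of adverse events. This limits the harm, but it is also how one occurrence can come to sit in two arms.

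4. *These are background tables.* Neither measure is a safety endpoint in Section 3.3, and no test or confidence interval is planned. This stands and keeps the point minor.

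5. *The 6.3.3 heading proves little.* It also covers demographics and medical history, which are summarised in mITT without difficulty. Those describe women before dosing, however, so grouping them as randomised is natural. Vital signs and examinations are repeated after dosing, and 8.12 summarises change from baseline. Nor does placement outside Section 8.11 alter what the data are.

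**Conclusion.** The inconsistency is real in v2.0 and v2.1, and minor. Safety measurements taken after dosing are assigned to a population grouped as randomised and designated primary for efficacy, while an as-treated set with the same members exists and is used for adverse events.

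The bounds of 1.8 points (placebo) and 0.9 points (VGX-3100X) apply to 8.13 only. They are maxima per mis-dosed woman with an abnormal finding, and they rest on all 165 women being dosed and examined. With fewer women examined at a visit, each one weighs somewhat more.

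Two stronger readings are not supported. A reader might take arm sizes of 132 and 66 from the 198 women of v3.0, but the wording at issue is confirmed only in the versions that randomise 165. A reader might also infer that the trial's safety conclusions are distorted. The main adverse event comparison already uses the safety set, and with no dosing error every table is the same under either population.

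**What to change.** In Sections 8.12 and 8.13, replace the mITT population with the safety analysis set, by treatment received. Before editing, check whether Section 8 of v3.0 keeps the old wording; if it has already been changed, nothing is needed.

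The cost is two phrases. No woman is added or dropped, no data collection changes, and there is no effect on sample size, power or the efficacy analysis. A rule for classing women with mixed exposure can be left to the SAP.
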